The primary endpoint, key secondary and other time-to-event efficacy endpoints will be evaluated in the ITT population. Other secondary efficacy analyses will be performed on the FAS population. Supportive analyses will be performed on the Per Protocol population. A sensitivity analysis will be performed for the primary endpoint and other time to event efficacy endpoints in the FAS population. The primary study analysis will be performed to demonstrate an effect on the primary endpoint. It will be calculated by means of the stratified log-rank test selecting the randomisation values of the stratification factors. The randomisation stratification factors are Geographical Region (Europe *versus* Rest of the World), Charlson Comorbidity Index (0-1 *versus* >1) ([Appendix 11 – Age-adjusted Charlson Index](#)) and Barthel index (≥ 90 *versus* <90) ([Appendix 7 - Barthel Index for Functional Assessment](#)). An unstratified log-rank test will also be calculated as a sensitivity analysis. A stratified Cox regression, with treatment as the single covariate, will be used to assess the magnitude of the treatment effect (i.e., the hazard ratio, HR) between the treatment arms comparisons. Cox regression will also be used to evaluate the influence of the stratification variables and other potential prognostic factors on the time-to-event efficacy endpoints. Time-to-event variables and their set time estimates will be analysed according to the Kaplan-Meier method. The main analysis will be adjusted for multiplicity using the Hochberg step-up procedure to preserve the type I error rate in the comparison of each dose of plitidepsin *versus* control arm. A futility analysis for efficacy/safety will be performed when 33% of events have been reached. The rho family of beta-spending functions (with $\rho=1.18$) will be used for the calculation of the stopping boundaries for futility in order to control type II error. If the accrual in any of the experimental arms is stopped after the interim futility analysis, the final analysis for the primary endpoint in the remaining arms will be performed at the 1.25% level using a Bonferroni-adjusted type I error rate.

Safety analyses will be based on the As Treated Population. All safety parameters will be summarised and also listed by treatment group and patient.

TABLE OF CONTENTS

SYNOPSIS	3
TABLE OF CONTENTS	16
LIST OF TABLES AND FIGURES	18
LIST OF ABBREVIATIONS.....	19
1. INTRODUCTION	21
1.1. Study Rationale	23

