3. INVESTIGATION PLAN

3.1. Overall Study Design and Plan Description

An overview of study design is shown in [Figure 1](#). This is a multicentre, open-label, controlled Phase 3 study in which adults requiring hospital admission and O₂ supplementation for management of moderate COVID-19 infection will be randomised in 1:1:1 to:

- Plitidepsin 1.5 mg arm: Patients will receive plitidepsin 1.5 mg/day intravenous (IV) in addition to dexamethasone on days 1 to 3 ([See Section 5. Study treatments](#)).
- Plitidepsin 2.5 mg arm: Patients will receive plitidepsin 2.5 mg/day IV in addition to dexamethasone on days 1 to 3 ([See Section 5. Study treatments](#)).
- Control arm: Patients will receive dexamethasone IV on Days 1 to 3. Additionally, in accordance with local treatment guidelines, patients in this group may receive a regulatory-approved antiviral treatment ([See Section 5. Study treatments](#)).

Randomisation will be stratified for 3 factors:

- a) Geographical Region (Europe *versus* Rest of the World);
- b) Charlson Comorbidity Index (0-1 *versus* >1) ([Appendix 11 – Age-adjusted Charlson Index](#)); and
- c) Barthel Index (≥ 90 *versus* <90) ([Appendix 7 - Barthel Index for Functional Assessment](#)).

[figure not shown]
From treatment initiation on Day 1, patients will be followed in the hospital for at least 4 days and then through Day 31 (± 3 days) or resolution/stabilisation of treatment-related adverse events, treatment-emergent adverse events of special interest, and SAEs. Patients discharged from the hospital prior to Day 8 will return to an out-patient clinic for assessments on Days 8 (± 1 day) and 31 (± 3 days). On Day 15 (± 1 day), patients will be followed up in remote or on-site visit ([Appendix 5 – Schedule of Assessments](#)).

An Independent Data Monitoring Committee (IDMC) will oversee study conduct (safety and primary endpoint), including analysis of summary safety data as per the trial requirements.

The study is expected to randomise approximately 609 patients (203 in each arm) over a period of 20 months.

Patients will be considered to be on study from the signature of the informed consent form (ICF) until the end of the follow-up period, that is, completion of the protocol-specified follow-up visit on Day 31 (± 3 days) or until resolution/stabilisation of treatment-related AEs, treatment-emergent adverse events of special interest, and SAEs that occurred through Day 31, whichever is longer.

Figure 1. Schema of the Study

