4.4.4. Replacement Procedures

No formal replacement of patients is foreseen. As the primary analysis of the study will be conducted in the Intent-to-Treat (ITT) population (see [Section 8.2.2](#)), the accrual will continue until 609 patients in the ITT population have been recruited.

4.4.5. Follow-up of Patients Prematurely Discontinued From the Study Treatment Regimen or Withdrawn From Study

Due to continued scientific importance of patient data even if study treatment is discontinued early, patients who withdraw from the study will be asked to complete all subsequent study procedures (follow-up/end of study visit), as described in the Schedule of Assessments ([Appendix 5](#)). Patients who are no longer hospitalised may complete their assessments by telephone or other means of remote communication.

Treatment-related adverse events, treatment-emergent adverse events of special interest, and SAEs that are ongoing at the time of discontinuation, or that develop before the protocol-specified Day 31 (± 3 days) follow-up visit, will be followed until resolution or stabilisation.

Steps will be taken by the sites to ascertain vital status in all randomised patients (e.g., with a vital records search) up through Day 31.

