8.2. Analysis Populations

Analysis of the primary and other time-to-event efficacy endpoints will be performed in the ITT population. Other secondary efficacy endpoints will be based on the FAS population. Supportive analyses will be performed on the Per Protocol population. A sensitivity analysis will be performed for the primary endpoint and other time-to-event efficacy endpoints in the FAS population, Safety endpoints analyses will be based on the Safety population.

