8.2.1. Intent-to-Treat (ITT) Population

All patients randomised in the trial, regardless of whether they received treatment.

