8.2.2. Full Analysis Set (FAS) Population

All randomised patients who have taken at least 1 dose of study treatment (plitidepsin or control) and with at least 1 postbaseline clinical status collected. FAS population will be analysed according to their randomised treatment.

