8.5. Efficacy Analysis

Analysis of the primary, key secondary and other time to event endpoints will be performed in the ITT population, and other secondary efficacy endpoints will be based on the FAS population. A sensitivity analysis will be performed for the primary endpoint and other time-to-event efficacy endpoints in the FAS population. Safety endpoints analyses will be based on the Safety population. Supportive analyses will be performed on the Per Protocol population.

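### Mortality and Day 8 WHO status are analysed in the FAS, so no stated mortality analysis covers all randomised patients although vital status is sought for all of them

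*Protocol*

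**What the plan says.** Synopsis, Statistical methods, assigns the primary, key secondary and other time-to-event efficacy endpoints to the ITT population and continues: "Other secondary efficacy analyses will be performed on the FAS population". Section 8.2 repeats this ("Other secondary efficacy endpoints will be based on the FAS population"), as does Section 8.5 ("other secondary efficacy endpoints will be based on the FAS population"). It is a fixed rule of the protocol, not a synopsis slip or a detail left to the SAP.

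Section 8.2.1 defines ITT as "All patients randomised in the trial, regardless of whether they received treatment". Section 8.2.2 restricts the FAS to randomised patients "who have taken at least 1 dose of study treatment (plitidepsin or control) and with at least 1 postbaseline clinical status collected".

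Section 2.2 lists Day 8 clinical status on the WHO scale as the first secondary efficacy endpoint. It lists mortality on Days 4, 8, 15 and 31 among the other secondary endpoints. Section 8.5.3 compares Day 8 status by a proportional odds model with p-values. It restricts between-group comparisons of binary endpoints to Day 8, with descriptive statistics at each visit.

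Section 4.4.5 states: "Steps will be taken by the sites to ascertain vital status in all randomised patients", through Day 31. Section 3.1 describes the design: "This is a multicentre, open-label, controlled Phase 3 study". Section 5.2 places randomisation before the first infusion.

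**The concern.** Entry to the FAS depends on two things that happen after randomisation: receiving a dose and having a status recorded. When everyone knows the allocation, either can be influenced by the arm. A patient or clinician may react differently to an investigational infusion with premedication than to dexamethasone with or without an approved antiviral. If the patients who drop out of the FAS have a different prognosis from those who stay, and drop out in different numbers by arm, the comparison is no longer the randomised one.

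Mortality is where this is hardest to justify. The protocol goes to the trouble of seeking vital status for everyone randomised, then names no mortality analysis that uses everyone. With few deaths expected, leaving out one or two can visibly move the ratio.

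**Working it through.** **Step 1: which set applies to which endpoint.**

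- Primary, key secondary and other time-to-event endpoints (for example, time to intensification of respiratory support): ITT, with FAS as sensitivity (Section 8.5).
- Mortality on fixed days, Day 8 WHO status, and percentages for ICU, oxygen, ventilation and readmission: FAS. No ITT sensitivity analysis is stated for these.
- Supportive efficacy analyses: Per Protocol, a subset of the FAS (Section 8.2.3).
- Deaths as a safety endpoint: As Treated, meaning exposed patients only (Sections 8.2.4 and 8.7).

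A randomised patient who receives no study treatment and dies is thus in none of the FAS, Per Protocol or As Treated sets. A treated patient who dies with no clinical status recorded after baseline is in As Treated but not in the efficacy mortality analysis.

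**Step 2: how much exclusions can move the result.** The protocol gives no planned figure for this, so the calculation is illustrative.

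Inputs:
- n = 203 per arm (Section 8.1).
- m = true Day 31 mortality in both arms = 4.5%. This matches the phase 1 study in Section 1.2, Table 3: 2/44 = 4.5%.
- k = plitidepsin-arm patients outside the FAS, and q = their death risk. Both are assumed.
- No control patient excluded (assumed) and no true treatment effect.

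Formula: apparent FAS mortality = (m × n − k × q) / (n − k), and risk ratio = that value / m. The expected deaths are 0.045 × 203 = 9.135 per arm.

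| k | q | Calculation | FAS mortality | Risk ratio |
|---|---|---|---|---|
| 2 | 10% | (9.135 − 0.2)/201 | 4.45% | 0.99 |
| 5 | 20% | (9.135 − 1)/198 | 4.11% | 0.91 |
| 10 | 20% | (9.135 − 2)/193 | 3.70% | 0.82 |
| 10 | 0% | 9.135/193 | 4.73% | 1.05 |

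**Step 3: direction.** From the formula, the ratio falls below 1 only when q > m and rises above 1 when q < m. Early deteriorators left out of a plitidepsin arm would flatter it. Refusers or early improvers left out would do the reverse, as the last row shows. Exclusions from the control arm would act in the opposite sense. With no exclusions there is no bias.

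**The case against.** There is a serious case that this matters little.

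- **Few patients may be affected.** Section 5.2 has screening and randomisation on the same day or within two consecutive days, and Section 7.4.2.1 lists randomisation on Day 1, the first dosing day. In the phase 1 study, Section 1.2 reports 45 randomised and one unable to complete treatment, after the infusion had begun. That gives no support for a 5% non-dosing rate. It does not exclude one either: with 0 of 45 undosed, the rule of three gives an upper bound of about 3/45 = 6.7%. This stands as a reason to expect a small effect.
- **Imbalance between arms is not shown.** A reader might infer that more plitidepsin patients will go undosed, partly because of QT restrictions. The QT criteria in Section 4.2 apply to all arms before randomisation, and the QTc rules in Section 4.4.2 concern withdrawal from treatment. Sections 5.1 and 8.4 also treat dexamethasone as study treatment, and every arm receives it on Day 1. The FAS wording leaves open whether a plitidepsin-arm patient given only dexamethasone counts as dosed. Imbalance is possible, not established.
- **The illustration is for Day 31, but the planned comparison is at Day 8.** Section 8.5.3 makes later mortality descriptive, and Table 3 of the phase 1 study reports no deaths by Day 7 or Day 15. The 0.82 also rests on about 7 versus 9 deaths, with an approximate 95% interval of 0.3 to 2.1. This stands: the figure shows sensitivity, not an expected bias.
- **Vital status supplies death only.** It does not supply oxygen use, ICU stay or non-fatal WHO category for undosed patients. This stands and limits the fix.
- **Mortality on a given day might be read as a set-time estimate of a time-to-event variable, hence ITT.** This does not hold. Section 2.2 lists no time-to-death endpoint, and Section 8.5.3 deals with binary endpoints separately. It could not cover Day 8 status in any case.

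**Conclusion.** The concern holds as a matter of population choice. Three places put mortality and Day 8 WHO status on a set defined by post-randomisation conditions in an open-label trial, and no stated mortality analysis includes everyone randomised.

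The size and direction of any resulting bias cannot be determined from the protocol. The risk ratios of 0.99, 0.91 and 0.82 rest on assumed exclusion counts, assumed mortality among those excluded, and a fully retained control arm.

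Two stronger conclusions are tempting and are not supported. One is that the FAS will favour plitidepsin: the protocol gives neither a non-dosing rate nor the prognosis of undosed patients. The other is that the trial's main result is compromised: the primary, key secondary and other time-to-event endpoints already use ITT and are unaffected. This is a worthwhile, inexpensive improvement to the secondary analyses.

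**What to change.** In the Synopsis (Statistical methods), Section 8.2 and Section 8.5:

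- Make ITT the main set for mortality and for Day 8 WHO status. Score death as 10, as Appendix 13 already does, and use the SAP's missing-data rule for other missing categories (Section 8.3 already defers imputation to the SAP).
- Do the same for the other yes/no clinical endpoints where data are collected.
- Keep FAS as the sensitivity set, mirroring the primary endpoint. Leave laboratory and viral-load endpoints on FAS, since they need samples.

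The cost is wording in three places and imputation for a few patients whose non-fatal status is missing. The 609 patients, the 530 events and the error rates do not change. If nearly everyone is dosed and assessed, ITT and FAS results will almost coincide. The open question of whether dexamethasone alone counts as a dose would then affect only the sensitivity analysis of these endpoints.

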	Time to sustained (i.e., with no subsequent readmission to Day 31) hospital discharge (since randomisation), before (protocol v.6) and after the amendment (protocol v.7).

Methodology/study design:

This is a multicentre, open-label, controlled Phase 3 study in which adults requiring hospital admission and O₂ supplementation for management of moderate COVID-19 infection will be randomised in 1:1:1 to:

- Plitidepsin 1.5 mg arm: Patients will receive plitidepsin 1.5 mg/day intravenous (IV) in addition to dexamethasone on days 1 to 3 ([See Section 5. Study treatments](#)).
- Plitidepsin 2.5 mg arm: Patients will receive plitidepsin 2.5 mg/day IV in addition to dexamethasone on days 1 to 3 ([See Section 5. Study treatments](#)).
- Control arm: Patients will receive dexamethasone IV on Days 1 to 3. Additionally, in accordance with local treatment guidelines, patients in this group may receive a regulatory-approved antiviral treatment ([See Section 5. Study treatments](#)).

Randomisation will be stratified for 3 factors:

- a) Geographical Region (Europe *versus* Rest of the World);
- b) Charlson Comorbidity Index (0-1 *versus* >1) ([Appendix 11 - Age-adjusted Charlson Index](#)); and
- c) Barthel Index (≥ 90 *versus* <90) ([Appendix 7 - Barthel Index for Functional Assessment](#)).

From treatment initiation on Day 1, patients will be followed in the hospital for at least 4 days and then through Day 31 (± 3 days) or resolution/stabilisation of treatment-related adverse events, treatment-emergent adverse events of special interest, and SAEs. Patients discharged from the hospital prior to Day 8 will return to an out-patient clinic for assessments on Days 8 (± 1 day) and 31 (± 3 days). On Day 15, patients will be followed up in remote or on-site visits ([Appendix 5 – Schedule of Assessments](#)).

An Independent Data Monitoring Committee (IDMC) will oversee study conduct (safety and primary endpoint), including analysis of summary safety data as per the trial requirements.

Number of patients:

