A total sample size of 609 patients (203 in each arm) with 530 events necessary for the analysis of the primary endpoint has been calculated based on a one-sided type I error rate of 1.25% (α -0.0125) with at least 80% power ($\beta=0.2$) to detect a target hazard ratio (HR) of 1.4 in the time to sustained withdrawal of supplementary oxygen, which means a decrease in the median time to the event from 8 days (control arm) to 5.7 days (plitidepsin). The sample size is adjusted for the multiple comparisons of each plitidepsin group with control group by a Bonferroni adjustment, although other advanced methods for correction of multiplicity will be used for the main analysis that will increase the power of the tests (<https://www.fda.gov/media/102657/download>). At the final analysis, if the HR is 1.27 or greater, in favour of any plitidepsin arm (equivalent to a decrease in the median time to sustained withdrawal of supplementary oxygen of 1.7 days or greater), then it is expected that the null hypothesis (i.e., $HR \leq 1$) will be rejected.

A futility analysis for efficacy/safety will be performed when 33% of events (sustained withdrawal of supplementary oxygen) have been reached. The rho family of beta-spending functions (with $\rho=1.18$) will be used for the calculation of the stopping boundaries for futility in order to control type II error. The stopping boundaries for the futility analysis will be calculated with the actual

number of events available in the Intent-To-Treat (ITT) population at that moment; if the number of events at the futility analysis is 116 in a pair comparison, the beta-spending corrected p-value to reject the alternative hypothesis should be higher or equal than 0.4199 and this p-value is associated with a $HR \leq 1.0382$.

If the recommendation of the IDMC is to discontinue one of the plitidepsin dosing arms at this futility analysis following the stopping rules, the study will continue from that point on a 1:1 randomisation fashion until the completion of the remaining treatment arms (203 patients per arm and 353 events of sustained withdrawal of supplementary oxygen in total necessary to perform the final analysis). The patients still ongoing in the dropped arm would continue to be followed up as per protocol and a Bonferroni-adjusted type I error rate of 1.25% will be kept for the comparison of the primary endpoint between the remaining plitidepsin arm and the control arm.

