8.5.1. Primary Efficacy Outcome Measures

Time-to event data (time to sustained withdrawal of oxygen supplementation) will be analysed using the Kaplan Meier method and presented with 95% CIs. A Cox regression model, including the levels of the randomisation stratification factors as covariates, will be applied to compare results between each dose of plitidepsin *versus* control arm. Hazard ratios, 2-sided 95% CIs, and p values for the comparison of each dose of plitidepsin *versus* control arm will be presented. The time-to-event between each dose of plitidepsin *versus* control arm will be compared using a 2-sided stratified log-rank test. The model will be adjusted for the randomisation stratification factors, i.e., Geographical Region (Europe *versus* Rest of the World), Charlson Comorbidity Index (0-1 *versus* >1) ([Appendix 11- Age-adjusted Charlson Index](#)) and Barthel index (≥ 90 *versus* <90) ([Appendix 7 – Barthel Index for Functional Assessment](#)). An unstratified log-rank test and Cox regression model will also be analysed as a sensitivity analyses. For both stratified and unstratified models, the hazard ratios, 2-sided 95% CIs, and p-values for the comparison of each dose of plitidepsin *versus* control arm will be presented. Proportional hazard assumption will be checked by means of a Cox regression including treatment and its interaction with time.⁴⁹ In case of strong rejection of proportionality, then restricted mean survival estimates and weighted log-rank tests (if applicable) will also be calculated in a sensitivity analysis in addition to HR.⁵⁰ The main analysis will be adjusted for multiplicity using the Hochberg step-up procedure to preserve the type I error rate in the comparison of each dose of plitidepsin *versus* control arm. If the accrual in any of the experimental arms is stopped after the interim futility analysis, the final analysis for the primary endpoint in the remaining arms will be performed at the 1.25% level using a Bonferroni-adjusted type I error rate.

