8.5.2. Key Secondary Efficacy Outcome Measures

Time-to event data will be analysed using the Kaplan-Meier method and presented with 95% CIs. A Cox-regression model, including the levels of the randomisation stratification factors as covariates, will be applied to compare results between each dose of plitidepsin *versus* control arm. Hazard ratios, 2-sided 95% CIs, and p-values for the comparison of each dose of plitidepsin *versus* control arm will be presented.

In the event that the primary endpoint is significant for both doses, the Hochberg procedure will be used to test the key secondary efficacy endpoints at the overall (2-sided) significance level of 0.05. This adjustment will not apply if the accrual in any of the experimental arms is stopped after the interim futility analysis. Details will be provided in the SAP.

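### Kaplan-Meier is fixed for time to weaning and time to discharge, with no statement that a patient who dies first counts as never recovered

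*Protocol*

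**What the plan says.** The synopsis (Statistical methods) covers all time-to-event variables: "Time-to-event variables and their set time estimates will be analysed according to the Kaplan-Meier method". Section 8.5.1 says that the primary endpoint "will be analysed using the Kaplan Meier method and presented with 95% CIs". Section 8.5.2 says the same of the key secondary endpoint: "Time-to event data will be analysed using the Kaplan-Meier method and presented with 95% CIs". A Cox model goes with both endpoints, and a stratified log-rank test with the primary.

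Section 8.5.1 also lists unstratified versions, a proportional-hazards check and, if proportionality is strongly rejected, restricted mean and weighted log-rank sensitivity analyses. None of these deals with death.

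The protocol names no cumulative incidence or other competing-risk method. It does not say whether a patient who dies before weaning or discharge is censored at death or carried to Day 31 as not recovered. Death appears elsewhere as a mortality endpoint, a safety endpoint and score 10 on the WHO scale (Section 2.2, Appendix 13). Section 4.4.5 has sites establish vital status to Day 31 for every randomised patient.

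**The concern.** A patient who dies on oxygen will never be weaned. Kaplan-Meier in its ordinary form ends that patient's follow-up at death and treats them as exchangeable with those still at risk, so they are credited with recovering later at the survivors' rate. One minus Kaplan-Meier is then not the proportion weaned or discharged.

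Two things could be affected. The first is the percentage reported as recovered at Day 15 or Day 31. The second is the between-arm comparison, which uses the same risk sets: if one arm loses more slow recoverers to death, its remaining risk set becomes enriched with fast recoverers. For a benefit claim that is the wrong direction.

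**Working it through.** **1. The plan's own figures.** Inputs from the synopsis and Section 8.1: one-sided alpha 0.0125, at least 80% power, HR 1.4, medians 8 and 5.7 days, 353 events per pairwise comparison.

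- Schoenfeld: 4(2.2414 + 0.8416)² / (ln 1.4)² = 336 events. Freedman gives 343.
- Power at 353 events is 0.821 without the futility look. It is 0.800 with the look at 116 events and bound HR 1.0382.
- 353 × 1.5 = 529.5, hence 530.
- Critical HR: exp(2 × 2.2414 / √353) = 1.269, stated as 1.27.

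The design figures hold and are not in dispute.

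**2. Recovery percentages if deaths are censored at death.** Constant hazards are assumed. Recovery hazard λ = ln 2 / 8 (control) or 1.4 × ln 2 / 8 (plitidepsin, median 5.7). The death hazard μ is solved so that μ/(λ+μ) × (1 − exp(−31(λ+μ))) equals the assumed Day 31 mortality.

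- 1 − KM = 1 − exp(−λt)
- Cumulative incidence = λ/(λ+μ) × (1 − exp(−(λ+μ)t))

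Mortality inputs: the pilot had 2/44 = 4.5% by Day 31 (Section 1.2, Table 3). The Introduction gives three deaths, 6.7%, but the Table 3 notes place one of them on Day 57. The pilot mixed severities, and the protocol gives no rate for this trial, so 2% is added as an assumed lower value.

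Example (control, 4.5%): λ = 0.0866 and μ = 0.00435. Incidence = 0.9522 × (1 − exp(−2.821)) = 0.895, against 1 − KM = 1 − exp(−2.686) = 0.932.

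| Day 31 mortality | Control 1−KM | Control incidence | Gap | Plitidepsin 1−KM | Plitidepsin incidence | Gap |
|---|---|---|---|---|---|---|
| 2% | 93.18 | 91.57 | 1.61 | 97.67 | 95.85 | 1.82 |
| 4.5% | 93.18 | 89.54 | 3.64 | 97.67 | 93.56 | 4.11 |
| 6.7% | 93.18 | 87.75 | 5.43 | 97.67 | 91.53 | 6.14 |

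At 4.5% and n = 203 the Day 31 gaps are 1.7 and 2.4 standard errors. At Day 15 they are 1.8 and 2.6 points (0.6 and 0.9 standard errors). With equal mortality the difference between arms hardly moves: 97.67 − 93.18 = 4.49 points by Kaplan-Meier, 93.56 − 89.54 = 4.02 by incidence.

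**3. The test, no true effect on weaning.** Simulation with 203 per arm, one-sided 1.25%, deaths only among slow recoverers. The slow-recoverer mixtures are assumptions.

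| Setting | Deaths, control v plitidepsin | Censored at death | Kept at risk to Day 31 |
|---|---|---|---|
| 20% slow (median 25 days; others 6.5) | 4.5% v 9% | HR 1.03, rejection 2.6% (4,000 runs) | HR 0.97, 0.5% |
| 20% slow | 4.5% v 4.5% | HR 1.00, 1.27% (8,000 runs) | not needed |
| 20% slow | 9% v 4.5% | HR 0.97, 0.4% (8,000 runs) | not needed |
| 25% slow (daily hazard 0.025; others 0.14) | 3.4% v 6.8% before weaning | HR 1.02, 1.9% (1,500 runs) | HR 0.98, 0.9% |
| 25% slow | 3.4% v 3.4% before weaning | HR 1.00, 1.0% (1,500 runs) | HR 1.00, 1.3% |

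A 600-run version of the first row gave about 2% and 0.7%. Monte Carlo error: √(0.026 × 0.974 / 4,000) = 0.25 points in the first row and √(0.0187 × 0.9813 / 1,500) = 0.35 points in the fourth. In the fourth row the Day 31 Kaplan-Meier percentages are 88.3 v 89.4, while 86.1 v 84.7 actually recovered, so the order of the arms reverses.

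**The case against.** The protocol never says that deaths are censored at death. Section 8 leaves specific details to the SAP, where censoring rules usually sit. Kaplan-Meier, log-rank and Cox are all compatible with a sound rule: if the dead stay at risk to Day 31 and nothing else is censored, one minus Kaplan-Meier equals the cumulative incidence. The endpoint itself (WHO score 4 or below, death being 10) fits that reading, although it sets no censoring time. All of this stands, and it makes the point conditional.

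A reader might infer that every reported recovery rate will be too high, or that the primary test is inflated. The documents support neither. The first needs censoring at death. The second also needs unequal mortality concentrated in slow recoverers, and the pilot gives no sign of that: Day 31 deaths were 1, 0 and 1 across its three doses, with no control arm. If control had the excess of deaths, censoring would be conservative. Mortality and WHO categories are also reported on Days 4, 8, 15 and 31, and the IDMC follows deaths by arm, so an excess would be visible.

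Nor is the whole distance between the two rules bias. With a patient-level HR of 1.27 in the 20%-slow setting, the marginal HR is 1.21 if nobody dies, 1.26 with deaths (4.5% v 9%) censored and 1.16 with the dead kept. About half of the distance is inflation. The rest comes from letting death count against recovery, which is an estimand choice.

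The objection does not remove the stated choice: a survival estimator is fixed for set-time recovery percentages, in a section detailed enough to list its sensitivity analyses, with nothing that accounts for death.

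**Conclusion.** The point holds as a conditional weakness in a stated estimator, worth correcting but not a demonstrated error in the primary test. If deaths are censored at death, Day 31 recovery percentages are overstated by 1.6 to 6.1 points across 2% to 6.7% mortality, assuming constant hazards and the planned medians. With equal mortality the log-rank test keeps its level. With assumed deaths of 4.5% v 9%, all among slow recoverers, the HR is about 1.03 and one-sided rejection about 2 to 2.6% under no effect, against 1.25%. This does not concern how a patient who dies after weaning is counted.

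**What to change.** In the synopsis and Sections 8.5.1 and 8.5.2:

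- report curves and set-time percentages as cumulative incidence (Aalen-Johansen) with death before the event as the competing event;
- state that in the log-rank test and Cox model patients who die before the event stay at risk to Day 31 as never weaned or discharged, and that the hazard ratio is read accordingly;
- show censoring at death as a sensitivity analysis.

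If the SAP already has this rule, align the protocol with it. In an open-label trial the rule should be fixed before results are seen.

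The cost is a few sentences and a little code, since vital status is already collected. Recovery rates fall by the gaps above, and the hazard ratio and power become slightly less favourable: in a 600-run simulation with slow recoverers, equal 4.5% mortality and patient-level HR 1.4, the HR moves from 1.34 to 1.31 and power from 65% to 58%. Those power levels reflect the assumed mixture; the change between the two rules is what matters here.
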